9.10 Heart rate and sympathetic nerve function

A secondary objective of the RATE-AF trial is to compare heart rate control in patients randomised to beta-blockers and digoxin using 24-hour ambulatory ECG. However, heart rate is not only affected by therapy, but also intrinsic variability in control by the autonomic nervous system. Sympathetic activity is elevated in cardiovascular conditions and could have a profound effect on heart rate response in individual patients, potentially masking the effects of therapy.¹⁰⁰ The proposed assessment uses a fine Tungsten needle (human hair width) that records nerve activity from a sympathetic nerve, performed at the baseline visit and then at the final up-titration visit. MSNA is an established research investigation which is virtually painless, safe and allows direct measurement of sympathetic tone. Our team have successfully used this technique in a range of conditions.^{101, 102}

10-15 patients from each treatment group will be asked to participate in a sub-study of muscle sympathetic nerve activity (MSNA). Patients will be selected that lack existing impairment (or potential impairment) of the nervous system, excluding those with diabetes, other medical conditions affecting autonomic function (for example, Sjogren's syndrome, systemic lupus erythematosus and rheumatoid arthritis), prior stroke and previous neurological conditions (Parkinson's disease, dementia, multiple sclerosis or Guillain-Barre syndrome). Potential participants will be given a specific Patient Information Leaflet written by the RATE-AF Patient and Public Involvement Team, and asked to sign the RATE-AF optional consent form.

Protocol:

Patients will be studied supine, in uniform conditions in a clinical environment. They will be monitored with continuous heart rate and beat-to-beat blood pressure in response to handgrip exercises and other simple sympathetic stimulation exercises (Portapres, Finapres Medical Systems). Recordings of postganglionic, multiunit MSNA will be obtained using a sterile 200µm tungsten microelectrode placed into the peroneal nerve at the fibular head and a reference electrode inserted subcutaneously at a site 2–3 cm distal. Prior to digitization, raw signals are

amplified ($\times 100,000$), filtered (bandwidth 700–2000Hz), rectified and integrated (time constant 100ms), in order to obtain a mean voltage sympathetic neurogram.

Recovery:

No recovery period is required; patients can immediately mobilise after the assessment is complete. Rarely, some patients may exhibit temporary leg/foot paraesthesia which settles spontaneously.

Objectives and analysis:

The objectives of this sub-study are exploratory – our hypothesis is that MSNA will identify a subset of patients with autonomic dysfunction that have an altered or distinct response to rate control therapy.

Change in sympathetic activity from baseline to after treatment with rate control will be analysed in comparison to change in heart rate to understand if sympathetic activity broadly interacts with treatment effects. The results will be used as pilot data to formulate a new research study investigating the role of autonomic dysfunction and outcomes in patients with AF. An analysis plan for this sub-study will be agreed before access to data.

10 Pharmacovigilance

Definitions of different types of AE are listed in **Table 2**. The Investigator should assess the seriousness and causality (relatedness) of AEs experienced by the participant (this should be documented in the source data). For further information please refer to **Section 10.1**.

Table 2: Standard AE Definitions

Term	Definition
Adverse Event (AE)	Any untoward medical occurrence in a patient or clinical trial participant administered a medicinal product and which does not necessarily have a causal relationship with this treatment
Adverse Reaction (AR)	Any untoward and unintended response in a participant to an investigational medicinal product which is related to any dose administered to that participant
Serious adverse event (SAE), serious adverse reaction (SAR) or unexpected serious adverse reaction	Any adverse event, adverse reaction or unexpected adverse reaction, respectively, that: 
 • results in death; • is life-threatening; • requires hospitalisation or prolongation of existing hospitalisation; • results in persistent or significant disability or incapacity; or • consists of a congenital anomaly or birth defect
Unexpected Adverse Reaction	An adverse reaction the nature and severity of which is not consistent with the information about the medicinal product in question set out: 
(a) in the case of a product with a marketing authorisation, in the summary of product characteristics for that product;
 
(b) in the case of any other investigational medicinal product, in the investigator's brochure relating to the trial in question.

SUSAR	Suspected Unexpected Serious Adverse Reaction

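### The nerve-activity sub-study's hypothesis is about who responds differently to rate control, but its one stated analysis relates two post-treatment changes and does not directly estimate that

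*Protocol*

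**What the plan says.** Protocol 9.10 motivates the sub-study by noting that sympathetic activity "could have a profound effect on heart rate response in individual patients, potentially masking the effects of therapy". Its hypothesis is that "MSNA will identify a subset of patients with autonomic dysfunction that have an altered or distinct response to rate control therapy". The analysis is given in one sentence: "Change in sympathetic activity from baseline to after treatment with rate control will be analysed in comparison to change in heart rate", and its purpose is "to understand if sympathetic activity broadly interacts with treatment effects".

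On size, "10-15 patients from each treatment group will be asked to participate in a sub-study of muscle sympathetic nerve activity", so 20-30 patients in all. MSNA is "performed at the baseline visit and then at the final up-titration visit". On selection, "Patients will be selected that lack existing impairment (or potential impairment) of the nervous system". On use, "The results will be used as pilot data to formulate a new research study".

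The section calls the objectives exploratory and leaves a detailed plan to be settled before anyone sees the data. It makes no power or precision claim. It names no baseline-MSNA term, no randomised-arm term and no heart-rate measure for the analysis. The SAP does not cover the sub-study.

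**The concern.** The motivation and the hypothesis both describe a patient characteristic that changes how a drug works in that patient. That calls for a marker fixed before treatment, related to the later response.

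The stated analysis uses change in MSNA, which is itself partly a response to the drug. Two problems follow. If baseline sympathetic state does alter the heart-rate response, subtracting baseline from follow-up weakens the signal. If the two drugs shift MSNA and heart rate by different average amounts, and the arms are pooled without adjustment, the two changes will be associated even though no patient characteristic modifies anything.

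At stake is the quality of the pilot estimate that the next study would be built on. No primary, secondary or safety conclusion of the main trial depends on it.

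**Working it through.** **No stated figure to reproduce.** Section 9.10 gives no power, effect size or SD.

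**Inputs from the documents.** 10-15 per arm, so N = 20 to 30 (Protocol 9.10). Significance level 0.05 (Protocol 12.3), taken as two-sided as in the main trial (Protocol 12.2).

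**Assumed, not in the documents.** Baseline MSNA (M0) has variance 1. Follow-up MSNA is 0.6 × M0 plus noise of variance 0.64, which also gives variance 1. Change in heart rate is b × M0 plus noise of SD 1, with b from 0.3 to 0.8.

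**Step 1: how much of M0 is left in the change.** Change in MSNA is D = −0.4 × M0 + noise, so Var(D) = 0.16 + 0.64 = 0.80. The correlation of D with M0 is −0.4/√0.80 = −0.447.

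**Step 2: correlations with change in heart rate.** For baseline MSNA, r = b/√(1 + b²). For change in MSNA, |r| is 0.447 times that.

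**Step 3: power.** Fisher's z approximation gives Φ(atanh|r| × √(N−3) − 1.96) + Φ(−atanh|r| × √(N−3) − 1.96).

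| b | r, baseline MSNA | r, change in MSNA | Power, change vs change (N = 20 / 30) | Power, baseline MSNA (N = 20 / 30) |
|---|---|---|---|---|
| 0.3 | 0.287 | 0.129 | 8% / 10% | 23% / 34% |
| 0.6 | 0.514 | 0.230 | 16% / 23% | 65% / 84% |
| 0.8 | 0.625 | 0.279 | 22% / 32% | 86% / 97% |

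Example, b = 0.8 and N = 30: atanh(0.279) × √27 = 0.287 × 5.196 = 1.49, and Φ(1.49 − 1.96) = 0.32. Simulating the same model gives about 9-32% and 22-96%, in line with the formula.

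**Step 4: dependence on the 0.447 link.** Take a marker-response correlation of 0.5. The stated comparison has 5% power (its significance level) if change in MSNA is unrelated to baseline, 18-26% if that link is 0.5 and 42-60% if it is 0.8. With a marker correlation of 0.7 and a link of 0.8 it reaches 74-91%. In the reverse case, where only the two changes are related (r = 0.5), it rejects in 64-82% and a baseline-MSNA analysis in 5%. The two analyses answer different questions.

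**Step 5: pooled arms with no modification.** If the arms differ by d in both changes, the shared arm shift adds d²/4 to the covariance and to each variance. With d = 1, r = 0.25/√(1.05 × 1.25) = 0.218, and the rejection rate is 15% (N = 20) to 21% (N = 30). With d = 0.5, r = 0.0625/√(0.8625 × 1.0625) = 0.065, and the rate is about 6% (6-7% across simulations). Including arm in the model returns it to about 5%.

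**Step 6: the arm-by-MSNA interaction.** For a two-by-two contrast of subset by arm, SE = √(sum of 1/cell size) in residual SDs. With 5 patients in each of four cells, SE = √0.8 = 0.894, and a 1 SD interaction has 18% power. Across subset shares of 20-50% and 10-15 per arm, the range is 13-26%. Reaching 80% power needs an interaction of 2.14 to 3.34 SD.

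**The case against.** The sub-study is labelled exploratory, its results are pilot data, it claims no power, and a fuller plan is to follow. Baseline MSNA and arm are recorded whatever the outline says, so the later plan could use them. All of this is right, and it limits the weight of the point. It does not remove it: the protocol already says what will be analysed, and a plan that follows the protocol takes over that comparison.

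The wording also names no correlation test and no pooling of arms. A reader might infer that the sub-study carries an inflated false-positive rate. The documents do not support that: the 15-21% figure needs a pooled, unadjusted test and a 1 SD arm difference in both changes, neither of which is stated.

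A reader might also infer that a true modifier would be found if only the analysis were replaced. That is too strong. At slope 0.3 the baseline analysis has only about 22-33% power, and the interaction has little power unless it is very large.

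Finally, the hypothesis does not say resting MSNA. Section 9.10 describes recording during handgrip and other stimulation, so dysfunction could be defined by reactivity. That stands, and it is a reason for the plan to say which baseline quantity is meant.

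**Conclusion.** The mismatch between hypothesis and stated analysis is in the text and needs no assumption. Its size does. With a baseline to follow-up MSNA correlation of 0.6 and slopes of 0.3-0.8, the stated comparison detects a real baseline relation in about 9-32% of trials, against about 22-96% for an analysis on baseline MSNA. The gap narrows when change in MSNA is very strongly tied to its baseline. The spurious-association figure holds only for pooled, unadjusted arms with large shifts.

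It would be wrong to conclude that the sub-study cannot answer its own question. The needed data are collected and the detailed plan is open; the outline simply does not yet say how the question will be answered. Since this is an exploratory pilot on which no main-trial result rests, the change is a useful improvement of low priority.

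**What to change.** In Protocol 9.10, and in the sub-study analysis plan before data access:

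- Make the main analysis a regression of change in heart rate on baseline MSNA, randomised arm and baseline heart rate, reported as estimates with 95% confidence intervals. State which baseline MSNA quantity is used.
- Add the arm-by-baseline-MSNA interaction as an estimate with its interval only, without a significance claim.
- Keep change in MSNA against change in heart rate as a mechanistic description, within arm or adjusted for arm.
- Name a heart-rate measure that has a baseline value. The 24-hour ambulatory rate does not qualify, because SAP 9.6 (change in heart rate) says it is taken only once.

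The cost is a few sentences. Baseline MSNA, arm and heart rate are already planned, so no recordings are added. The drawback is a wide interval for the interaction with 20-30 patients, which the report should show openly.

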10.1 Recording and Assessment of Adverse Events

Targeted adverse events as they appear on the CRF will be reportable to the **RATE-AF** Trial Office up to 30 days post last IMP administration. Any SUSAR related to the IMP should to be reported irrespective of how long after IMP administration the reaction has occurred.

Adverse events will be recorded in the medical records and CRFs. Most AE/ARs that occur in this trial, whether they are serious or not, will be 'expected' treatment-related toxicities due to the drugs used in this trial.

Refer to **Table 3** for definition of expectedness.

Table 3: Expectedness

Category	Definition
Expected	An adverse event that is classed in nature as serious and which is consistent with the information about the IMP listed in the Investigator Brochure (or section 4.8 of the relevant SmPC if Licensed IMP) or clearly defined in this protocol
Unexpected	An adverse event that is classed in nature as serious and which is not consistent with the information about the IMP listed in the Investigator Brochure (or SmPC if Licensed IMP)

Adverse events will be recorded with clinical symptoms and accompanied with a simple, brief description of the event, including dates as appropriate.

The assessment of relationship of adverse events to the administration of IMP is a clinical decision based on all available information at the time. The following categories as outlined in **Table 4** will be used to define the causality of the adverse event.

Table 4: Categorisation of Causality

Category	Definition	Relatedness
Definitely	There is clear evidence to suggest a causal relationship, and other possible contributing factors can be ruled out	Related
Probably	There is evidence to suggest a causal relationship, and the influence of other factors is unlikely	
Possibly	There is some evidence to suggest a causal relationship (e.g. the event occurred within a reasonable time after administration of the trial medication). However, the influence of other factors may have contributed to the event (e.g. the patient's clinical condition, other concomitant events)	
Unlikely	There is little evidence to suggest there is a causal relationship (e.g. the event did not occur within a reasonable time after administration of the trial medication). There is another reasonable explanation for the event (e.g. the patient's clinical condition, other concomitant treatments)	Not related
Not related	There is no evidence of any causal relationship	

The collection and reporting of Adverse Events (AEs) will be in accordance with the Medicines for Human Use (Clinical Trials) Regulations 2004 and subsequent amendments. The Investigator will assess the seriousness and causality (relatedness) of all applicable AEs experienced by the participant with reference to the reference safety information. This should be documented in the source data with reference to the approved reference safety information (Section 4.8, Undesirable Effects) of the SmPC for Digoxin (dated: 20th March 2014) and the reference safety information (Section 4.8, Undesirable Effects) of the SmPC for Bisoprolol (dated: 19th June 2015).

10.2 Non-Serious Adverse Events/ Adverse Reactions

Refer to Table 2 for definitions

Common adverse reactions (see Section 7.4) will be recorded on the relevant CRF and sent to the RATE-AF Trial Office.

10.3 Serious Adverse Events

Refer to Table 2 for definitions

All Serious Adverse Events (SAEs), that are not excluded from expedited reporting will be recorded in the hospital notes and should be reported to the **RATE-AF** Trial Office on a SAE Form. The completed form should be **faxed to the RATE-AF Trial Office on [name] or [name]**, as soon as possible and ideally within one working day of becoming aware of the event. The site Investigator should be able to respond to any related queries raised by the **RATE-AF** Trial Office as soon as possible.

10.3.1 Expected SAEs NOT to be Reported on a SAE Form

Expected SAEs are those listed in the current SmPC for the trial IMPs and can be excluded from the expedited reporting outlined in **Section 10.1**, for example if they are expected to occur on a regular basis, are no more severe and offer no further new information to the safety profile. These events should continue to be recorded in the source data and relevant CRFs.

In addition, events **NOT** considered to be SAEs are hospitalisations for:

- Routine treatment or monitoring of the studied indication, not associated with any deterioration in condition
- Treatment, which was elective or pre-planned, for a pre-existing condition that is unrelated to the indication under trial, and has not worsened

Note: Death from any cause should be reported on an SAE Form and returned to the **RATE-AF** Trial Office.

10.4 SUSARs

Refer to Table 2 for definitions

SAEs classed by as both suspected to be related to the trial IMP and unexpected are categorised as SUSARs, and are always subject to expedited reporting. An SAE Form should be completed, and faxed to the RATE-AF Trial Office within 24 hours of the research staff at site becoming aware of the event. The local investigator will provide the causality assessment.

The Chief Investigator (or nominated individual) will undertake urgent review of all such SAEs and may request further information immediately from the clinical team at site. Causality will be assessed by a medically qualified doctor who has been delegated the task and then reviewed by the local PI. The Chief Investigator will not overrule the causality or seriousness assessment given by the local investigator but may add additional comment on these. The Chief Investigator will provide the determination of expectedness according to the reference safety information.

SUSARs will be notified to the MHRA and REC by the RATE-AF Trial Office. SUSARs that are fatal or life-threatening will be notified to the MHRA and REC within 7 days after the RATE-AF Trial Office has been notified. Other SUSARs will be reported to the REC and MHRA within 15 days after the Trial Office has been notified.

10.5 Development Safety Update Reports

The RATE-AF Trial Office will provide the MHRA with Development Safety Update Reports (DSURs). The reports will be submitted within 60 days of the Developmental International Birth Date (DIBD) of the trial each year until the trial is declared ended.

10.6 Annual Progress Reports

An annual progress report will be submitted to the REC within 30 days of the anniversary date on which the favourable opinion was given, and annually until the trial is declared ended.

10.7 Pregnancy

Due to the age of participants that will be randomised into the RATE-AF Trial (≥ 60 years), it is highly improbable that female participants will be pregnant at the time of randomisation, or become pregnant during the trial. Any pregnancies will be followed up for outcome; any outcome meeting the definition of an SAE will be reported to the RATE-AF Trial Office on the relevant CRF.

10.8 Reporting Urgent Safety Measures

If any urgent safety measures are taken the Principal Investigator/BCTU/Sponsor shall immediately and in any event no later than 3 days from the date the measures are taken, give written notice to

the MHRA and the REC of the measures taken and the circumstances giving rise to those measures.

11 Quality Control and Quality Assurance

11.1 Site Set-Up and Initiation

All participating Principal Investigators will be asked to sign the necessary agreements and supply a current CV to the Trials Office. All members of the site research team will also be required to sign a site signature and delegation log. Prior to commencing recruitment all sites will undergo a process of initiation and will have completed GCP training. Key members of the site research team will be required to attend either a meeting or a teleconference covering aspects of the trial design, protocol procedures, Adverse Event reporting, collection and reporting of data and record keeping. Sites will be provided with an Investigator Site File containing essential documentation, instructions, and other documentation required for the conduct of the trial. The Trials Office must be informed immediately of any change in the site research team.

11.2 Central Monitoring

Monitoring of this trial will be to ensure compliance with Good Clinical Practice. A risk proportionate approach to the initiation, management and monitoring of the trial will be adopted (as per the MRC/DH/MHRA Joint Project: Risk-adapted Approaches to the Management of Clinical Trials of Investigational Medicinal Products) and outlined in the trial-specific risk assessment.

The Trials Office will be in regular contact with the site research team to check on progress and address any queries that they may have. The Trials Office will check incoming CRFs for compliance with the protocol, data consistency, missing data and timing. Sites will be asked for missing data or clarification of inconsistencies or discrepancies. Sites will be requested to send in copies of signed Informed Consent Forms and other documentation for in-house review for all participants providing explicit consent.

Additional on-site monitoring visits may be triggered, for example by poor CRF return, poor data quality, low SAE reporting rates, excessive number of participant withdrawals or deviations. This will be detailed in the monitoring plan. If a monitoring visit is required the Trials Office will contact the site to arrange a date for the proposed visit and will provide the site with written confirmation. Investigators will allow the **RATE-AF** trial staff access to source documents as requested.

11.3 Audit and Inspection

The Principal Investigator will permit trial-related monitoring, quality checks, audits, ethical reviews, and regulatory inspection(s) at their site, providing direct access to source data/documents. The Principal Investigator will comply with these visits and any required follow up. Sites are also requested to notify the Trials Office of any MHRA inspections.

11.4 Notification of Serious Breaches

In accordance with Regulation 29A of the Medicines for Human Use (Clinical Trials) Regulations 2004 and its amendments the Sponsor of the trial is responsible for notifying the licensing authority in writing of any serious breach of the conditions and principles of GCP in connection with that trial or the protocol relating to that trial, within 7 days of becoming aware of that breach.

For the purposes of this regulation, a “serious breach” is a breach which is likely to effect to a significant degree the safety or physical or mental integrity of the participants of the trial; or the scientific value of the trial. Sites are therefore requested to notify the Trials office of any suspected trial-related serious breach of GCP and/or the trial protocol. Where the Trials Office is investigating whether or not a serious breach has occurred sites are also requested to cooperate with the Trials Office in providing sufficient information to report the breach to the MHRA where required and in undertaking any corrective and/or preventive action. Sites may be suspended from further recruitment in the event of serious and persistent non-compliance with the protocol and/or GCP, and/or poor recruitment. Any major problems identified during monitoring may be reported to Trial Management Group and Trial Oversight Committee, the REC and the relevant regulatory bodies. This includes reporting serious breaches of GCP and/or the trial protocol to the REC and MHRA. A copy is sent to the University of Birmingham Clinical Research Compliance Team at the time of reporting to the REC and/or relevant regulatory bodies.

